5.3. Competing Risk Analysis

Competing risks arise when subjects are at risk of experiencing more than one cause of failure (event) and failure due to other causes precludes observing the main cause of interest (i.e. censored for primary efficacy composite endpoint).

The primary efficacy composite endpoint is defined as a composite of objectively confirmed symptomatic lower extremity proximal DVT, asymptomatic lower extremity proximal DVT, symptomatic lower extremity distal DVT, symptomatic upper extremity DVT, symptomatic non-fatal PE, incidental PE or VTE-related death (adjudicated by CEC). For this type of outcome (the primary endpoint), a death due to causes other than VTE-related is a competing risk event and, as such, a patient is no longer at risk of having any of the events of interest.

To account for competing risks (deaths from causes other than venous thromboembolism related; VTE-related deaths are included in the primary efficacy composite endpoint) in the primary efficacy analysis, a cumulative incidence approach will be followed with the use of Gray's (1988)⁹ two-sample test (two-sided alpha level, 0.05). Hazard ratios and 95% confidence intervals will be calculated with the use of the Fine and Gray (1999)¹⁰ regression model (with treatment group as a factor). Cumulative incidence functions (defined as the cumulative probability of failure from a specific cause over time) will be estimated separately for the two study groups. These analyses will be based on the '**Up-to-Day 180**' observation period for the ITT population with censoring as defined above in Section 2.6.

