1.5. Randomization and Blinding

A centralized randomization strategy will be implemented in this study. Subjects will be randomly assigned in a 1:1 ratio to 1 of 2 treatment groups based on a computer-generated subject-randomization schedule prepared by or under the supervision of the sponsor prior to initiation of the study. The randomization will be stratified by tumor type (Advanced Pancreatic Cancer [APC] or non-APC) such that up to approximately 25% of the subjects randomly assigned are those with APC. Using the randomization schedule, the IWRS will assign treatment. The IWRS will also provide the number of the study drug bottle to be dispensed for each randomly assigned subject on Day 1 and at each visit (except Day 180/End-of-Treatment) during the double-blind treatment period. The requestor must use his or her own user identification (ID) and personal identification number (PIN) when contacting the IWRS and will then be asked to provide relevant subject details to uniquely identify the subject. Based on these randomization codes, the study drug will be packaged and labeled in a manner that maintains the double-blinded nature of this study.

The investigator will not be provided with randomization codes. The codes will be maintained within the IWRS, which has the functionality to allow the investigator to break the blind for an individual subject.

Data that may potentially unblind the treatment assignment (ie, events that contribute to the primary and secondary outcome or treatment allocation) will be handled with special care to ensure that the integrity of the blind is maintained and the potential for bias is minimized. This can include making special provisions, such as segregating the data in question from view by the investigators, clinical team, or others as appropriate until the time of database lock and unblinding.

Pancreatic cancer subjects are at a higher risk to develop VTE (VTE Khorana risk score ≥ 2). These subjects are also more likely to discontinue early from the study. Therefore, higher than planned (25%) number of pancreatic subjects were allowed for enrollment into this study.

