5.2.2. Analysis Methods

The primary efficacy composite endpoint analysis will be based on the '**Up-to-Day 180' observation period for the ITT population** with censoring as defined in Section 2.6.

The cumulative distribution function of the time to first occurrence of the primary efficacy composite endpoint will be estimated by the Kaplan-Meier method. The primary statistical hypothesis will be tested using a log-rank test, stratified by tumor type (APC or non-APC).

The estimate of the hazard ratio (HR), RRR (RRR=100*[1-HR] %) and the 95% confidence intervals for the treatment effect will be provided based on a stratified Cox proportional hazard model (stratification factor: APC or non-APC) and including treatment group as a binary covariate (i.e., rivaroxaban, placebo).

The cumulative event rate derived from Kaplan-Meier estimate will also be displayed graphically to evaluate the timing of event occurrence and the consistency of the treatment effect over time.

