5.2.3. Supportive Analyses for Primary Efficacy Composite Endpoint

To assess the robustness of the conclusion of the primary analysis, supporting analyses of the primary efficacy composite endpoint will be performed based on different observation periods and analysis populations as described below with censoring rules defined in Section 2.6:

- Based on the '**On-Treatment**' **observation period** for the ITT population
- Based on the '**Up-to-Day 180**' **observation period** for the PP population
- Based on the '**On-Treatment**' **observation period** for the PP population
- Based on the '**Post-Randomization**' **observation period** for the ITT population
- Based on the '**Post-First Dose**' observation period for the ITT population

In all cases, the 2-sided 95% confidence interval (CI) for the hazard ratio (rivaroxaban vs placebo) will be provided using the stratified Cox proportional hazards model (stratification factor: APC or non-APC) and including treatment group as a binary covariate (i.e., rivaroxaban, placebo).

The cumulative event rate derived from Kaplan-Meier estimate will also be displayed graphically to evaluate the timing of event occurrence and the consistency of the treatment effect over time and tested using a log-rank test, stratified by tumor type (APC or non-APC).

Summary of Primary Efficacy Composite Endpoint Analysis Methods			
Endpoint	Observation Period	Analysis Population	Method
Primary Efficacy Composite Endpoint (CEC Adjudicated Events)	Primary Up-to-Day 180	ITT	Primary Analysis Kaplan-Meier Estimates (Cumulative event rates and stratified log-rank test) Cox-model (HR, 95% CI)
	Supportive On-Treatment	ITT	
	Up-to-Day 180	PP	
	On-Treatment	PP	
	Post-Randomization	ITT	
	Post-First Dose	ITT	
	Up-to-Day 180	ITT	Sensitivity Analysis 1. Include asymptomatic distal DVT 2. Dropout with no follow up – treating time to discontinuation as being time to an event.
	Up-to-Day 180	ITT	Competing Risk Analysis Deaths due to causes other than VTE-related will be a competing risk event Gray's 2-sample test (Cumulative Incidence Function) Fine and Gray regression model

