5.2.4. Subgroup Analyses for the Primary Efficacy Composite Endpoint

Analyses of the primary efficacy composite endpoint will also be performed to examine the consistency of treatment effect across subgroups listed in Section 2.7. Homogeneity of treatment effect will be evaluated using the same model as described in Section 5.2.2 (stratified Cox proportional hazard model with treatment as a covariate). Subgroup analysis will be performed if there are at least 30 total randomized subjects in each subgroup category. Only descriptive

summaries will be presented for subgroups with fewer subjects. *The subgroup analysis by race and ethnicity will be denoted as 'Not Reported' for subjects from France as this information is not collected from the sites due to local regulation.*

The interaction of treatment with each of the subgroups will be analyzed based a stratified Cox proportional hazard model with stratification factor and treatment group with additional terms for subgroup and subgroup-by-treatment interaction. Further evaluations will be performed to assess and explain the nature of the interaction (qualitative or quantitative) if a significant (p value <0.10) interaction is observed. Significant interactions will be examined using a two-sided Gail-Simon⁸ test. Descriptive statistics (n, mean, standard deviation, median, and range) will be presented by treatment groups for each subgroup.

The subgroup analyses of the primary efficacy composite endpoint will be based on the '**Up-to-Day 180**' observation period for the ITT population with censoring as defined in Section 2.6.

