5.2.5. Sensitivity Analyses

5.2.5.1. Additional Primary Efficacy Composite Endpoint – Include Asymptomatic Distal DVT

An additional composite efficacy endpoint will also be defined to *include the occurrences of 'asymptomatic lower extremity distal DVT'.*

Sensitivity analysis will be performed on the time to the first occurrence of objectively confirmed symptomatic lower extremity proximal DVT, asymptomatic lower extremity proximal DVT, symptomatic lower extremity distal DVT, asymptomatic lower extremity distal DVT, symptomatic upper extremity DVT, symptomatic non-fatal PE, incidental PE or VTE-related death as adjudicated by the independent Clinical Endpoint Committee (CEC). This analysis will be based on the ITT analysis population for the '**Up-to-Day 180**' observation period.

Cumulative distribution function of the time to first occurrence will be estimated by the Kaplan-Meier method and tested using a log-rank test, stratified by tumor type (APC or non-APC).

The estimate of the hazard ratio (HR), RRR (RRR=100*[1-HR] %) and the 95% confidence intervals for the treatment effect will be provided based on a stratified Cox proportional hazard model (stratification factor: APC or non-APC) and including treatment group as a binary covariate (i.e., rivaroxaban, placebo).

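### The competing-risk analysis of the primary composite leaves out the APC/non-APC randomization stratum that the primary, supportive, subgroup and sensitivity analyses use

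*SAP*

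**What the plan says.** Section 5.3 of the SAP treats death from causes other than VTE as a competing event. It specifies Gray's two-sample test at a two-sided level of 0.05 and a Fine-Gray "regression model (with treatment group as a factor". Treatment is the only term listed. The competing-risk row of the summary table in 5.2.3 repeats Gray's "2-sample test (Cumulative Incidence Function" and the Fine-Gray model, again without a stratum. Unlike 5.4.2 and 5.6.2, Section 5.3 does not refer back to the primary analysis approach, so stratification cannot be read in from there.

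For the same endpoint, the stratum appears in:

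- the primary analysis (5.2.2): "The primary statistical hypothesis will be tested using a log-rank test, stratified by tumor type (APC or non-APC", with a stratified Cox model;
- the supportive analyses (5.2.3): "treatment effect over time and tested using a log-rank test, stratified by tumor type (APC or non-APC", with a stratified Cox model;
- the subgroup models (5.2.4): "stratified Cox proportional hazard model with stratification factor and treatment group with additional terms for subgroup";
- both sensitivity analyses (5.2.5.1 and 5.2.5.2): "estimated by the Kaplan-Meier method and tested using a log-rank test, stratified by tumor type (APC or non-APC".

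Section 1.5 makes APC/non-APC the randomization stratum. It also states: "Pancreatic cancer subjects are at a higher risk to develop VTE". It adds that these subjects are more likely to discontinue early, and that a "higher than planned (25%) number of pancreatic subjects were allowed for enrollment into this study". No reason is given for leaving the factor out of 5.3.

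**The concern.** The competing-risk analysis exists to show whether non-VTE deaths change the primary result, so its estimate and p-value will be set beside the stratified hazard ratio and log-rank test of 5.2.2. The move from a cause-specific to a subdistribution hazard is the intended difference. Dropping a randomization factor that the SAP itself describes as prognostic is a second, unintended one. Omitting a prognostic factor from a hazard model generally pulls the treatment estimate toward 1 and gives up a little power. A reader could then attribute to competing deaths a shift that comes partly from the missing stratum.

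What is at stake is interpretation and a small loss of efficiency, not validity. The unstratified test keeps its type I error, and the analysis is not part of the hierarchy in 5.5.

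**Working it through.** **The plan's own figure.** The SAP states no figure for the competing-risk analysis, so I first reproduced the sample size in 1.4, which supplies the design inputs.

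- Hazard ratio: ln(1 − 0.06) / ln(1 − 0.145) = ln(0.94) / ln(0.855) = 0.395.
- Freedman events at 90% power: ((1 + 0.395)/(1 − 0.395))² × (1.96 + 1.2816)² ≈ 56.
- Subjects: 56 / ((0.145 + 0.06)/2) = 56 / 0.1025 ≈ 546. With 20% discontinuation, 546 / 0.8 ≈ 683, against the stated figure of about 700.
- Two-proportion power with 280 per arm (350 × 0.8): 91.5%, consistent with the stated >90%.

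The inputs are sound.

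**Main simulation: with or without the stratum.** There were 4,000 trials per scenario. VTE, death and dropout times were exponential, follow-up ended at Day 180, and allocation was 1:1 within stratum.

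- From the SAP: 800 subjects, pooled placebo VTE 14.5%, dropout 20%, design hazard ratio 0.395.
- Assumed, because the SAP gives no by-stratum rates and no death rate: 25–50% APC; APC-to-non-APC hazard ratios of 1.5–4 for VTE, 1.5–3 for death and 1.5–2 for dropout; non-VTE death 8–30% (8% and 30% at 33% APC only); treatment hazard ratios of 1.0 and 0.60 besides the design value.
- Fitted to each trial: the stratified cause-specific Cox model, and Fine-Gray with inverse-probability-of-censoring weights, unstratified and stratified. The Fine-Gray score test stands in for Gray's test.

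| Quantity | Result |
|---|---|
| Shift of mean subdistribution HR toward 1 when the stratum is dropped | 0.0003 to 0.008 |
| Example: 33% APC, VTE ratio 4, death 15% | 0.599 stratified, 0.605 unstratified |
| Power change from dropping the stratum, HR 0.60 | 0.1-point gain to 2.3-point loss |
| Power change from dropping the stratum, HR 0.395 | 0 to 0.5-point loss |
| Null rejection, unstratified | 4.1–5.4% |
| Null rejection, stratified | 4.4–5.6% |
| Mean gap, stratified Cox HR vs unstratified Fine-Gray HR | at most 0.010 |
| Share of that gap due to the stratum, APC VTE hazard 1.5 times | 16–55% |
| Share of that gap due to the stratum, APC VTE hazard 2.5–4 times | 41–86% |
| Effect of stratum-specific censoring weights on the subdistribution HR | at most 0.0001 |

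The Monte Carlo standard error of a null rejection rate is √(0.05 × 0.95 / 4000) = 0.34 points, so a single scenario at a true 5% would usually fall between about 4.3% and 5.7%.

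**Second simulation, set up differently.** This used the subdistribution score test and a Fine-Gray fit with known censoring times, at N = 700 or 800, 25% or 35% APC, APC-to-non-APC placebo risk ratios of 1 to 3, and 2,000–10,000 runs per setting.

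| Setting (25% APC) | Power, unstratified | Power, stratified |
|---|---|---|
| N = 800, HR 0.395, ratio 2, dropout 40%/15% | 96.1% | 96.2% |
| N = 700, HR 0.395, ratio 3, dropout 20% in both | 95.0% | 95.4% |
| N = 800, HR 0.70, ratio 1.5, dropout 40%/15% | 37.2% | 37.3% |
| N = 800, HR 0.70, ratio 2, dropout 40%/15% | 37.3% | 37.8% |
| N = 800, HR 0.70, ratio 3, dropout 40%/15% | 34.2% | 36.3% |

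At ratio 3 and the design effect the unstratified estimate was 0.395 and the stratified one 0.388. Null rejection was 4.4–5.0% unstratified and 4.7–5.2% stratified. With no prognostic difference between strata (ratio 1) there was no gain and no measurable loss.

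**Scale against sampling error.** At HR 0.60 with 400 per arm, expected events before losses are 400 × 0.145 + 400 × (1 − 0.855^0.6) = 58 + 36 = 94, so SE(log HR) ≈ √(4/94) = 0.21. The example shift is ln(0.605/0.599) = 0.010, about 5% of one standard error.

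**The case against.** The strongest reply is that nothing here is wrong. Section 5.3 and its table row agree with each other, the analysis is valid and supplementary, and the shift is about a twentieth of a standard error. The percentages quoted above are shares of a gap that is itself at most 0.010. All of this stands, and it is why the point is minor.

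The higher APC risk is also not quantified. Section 1.5 supports it by reference to a Khorana score of at least 2, which every enrolled subject must have. This stands too: the upper magnitudes are assumptions, and if the strata did not differ, stratifying would gain nothing. It would not cost anything measurable either.

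A stratified subdistribution hazard ratio is conditional on stratum, whereas the cumulative incidence curves in 5.3 are drawn by treatment group only. That is a reason to state which ratio is intended. The same holds for the primary analysis, where Kaplan-Meier curves accompany a stratified Cox model, so the curves can stay as they are.

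Finally, 5.3 is not the only place without a stratum. The non-proportional-hazards tests in 5.2.2.1 and the recurrent-bleeding analysis in 6.1.3 name none, and 5.4.2, 5.6.2 and 6.1.4.2 enter it as a Cox covariate. This is true, but it does not explain the omission from an analysis meant to be compared directly with the stratified primary result.

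**Conclusion.** The concern holds, as a minor point of consistency and efficiency. The omission is plain in the text and unexplained. Two differently built simulations agree on direction and size: a slight pull toward 1 when the stratum is omitted, a power benefit from stratifying of roughly 0 to 0.5 points at the design effect and up to about 2 points at weaker effects (HR 0.60 to 0.70), and null rejection near 5% either way. The 0.1-point power gain from dropping the stratum, seen at one end of the range, is too small to matter. The sizes rest on assumed stratum-specific VTE, death and dropout rates. The case for the change does not depend on them: analysing by the randomization stratum makes the competing-risk result directly comparable with the primary one and costs nothing in subjects or alpha.

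**What to change.** In Section 5.3, specify Gray's test stratified by APC/non-APC and a Fine-Gray model stratified by APC/non-APC with treatment as the covariate, and state that the estimate is reported as a subdistribution hazard ratio. Saying explicitly that the factor enters as strata settles which ratio is meant and matches the Cox model in 5.2.2. Make the competing-risk row of the 5.2.3 table agree. The cumulative incidence curves by treatment group can stay. Curves by stratum and stratum-specific censoring weights are optional.

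The cost is one sentence, one table row and a stratum term in the program, with no new data.

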2.5. Definition of Study Dates and Observation Period End Dates

The study dates and period end dates will be used to define the time period for data included in the analysis of efficacy and safety endpoints for the different observation periods (defined in Section 2.6).

Study Day 1 date: the date of randomization of the subject.

End-of-Study (EOS): the date of the last study-related procedure for the subject (EOS is defined as last assessment day during the study, including the Day 210/Post-Treatment Follow Up visit) and is defined as the minimum (last assessment day during the study, death date).

Double-Blind period start date will be the date of randomization.

Double-Blind period end date will be defined as the completion/early withdrawal date (date of completion or early withdrawal [any reason including death] from the double-blind period).

Up-to-Day 180 observation period end date will be defined as follows;

- Day 180/EODB completion date (for subjects who completed the double-blind period) or
- Death date (subjects who died during the double-blind period [DB reason=death] or during any time from randomization through Day 180 [died post withdrawal from DB but before Day 180/EODB visit] or
- Maximum (double-blind withdrawal date, randomization date + 180 days) for subjects who withdrew early from the double-blind period [any reason other than death] and had not died during the time from randomization through Day 180

First dose date: the date on which the first dose of study drug is taken by the subject. If missing or partial for a subject who takes study drug, the first dose date is set to the randomization date.

Last dose date: the date on which the last dose of study drug is taken by the subject (dose end date). If the dose end date is missing or partial for a subject who takes study drug, the last dose date is set as follows

- Maximum (Minimum (discontinuation date in the double-blind period [including death date during double-blind period], last visit date when drug is dispensed + number of pills dispensed - number of pills returned at following visit), imputed partial last dose date, exposure start date of last record))
 - Imputation rule for partial dates: If only the day is missing, then day imputed to the last day of that month. If day and month are missing, the date will be imputed to the start date if year is the same, else imputed to January 1st.

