2.6.1. Up-to-Day-180 Observation Period

This observation period includes data from randomization to Up-to-Day 180 end date (defined in Section 2.5).

Event: All efficacy events (with respect to deaths, *VTE-related deaths are counted as events for primary efficacy endpoint. For the secondary efficacy endpoints, all-cause deaths are counted as events*) that occurred from randomization through the Up-to-Day 180 end date (Section 2.5) will be included in the analysis of this observation period.

- Event time - The time to event is defined as the time from randomization to the time of the first event during this observation period.

Censoring: Subjects who did not experience an event during this observation period will be censored at the last day of their complete assessment for study outcomes.

Subjects who died during this observation period will be censored as of their death date for endpoint analyses not related to death.

- Censoring time - The time to censoring is defined as the time from randomization to the minimum of (last day of their complete assessment for study outcomes during the double-blind period [double-blind completion/withdrawal], death date [non VTE-related deaths for primary efficacy composite endpoint]).

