 - a. If subject experiences an efficacy composite endpoint event (primary or secondary, including VTE-related deaths) after withdrawing from the study and the time to the occurrence of the event is prior to Day 180, then this event and corresponding time to the occurrence of the event will be included in the analysis of primary efficacy composite endpoint. If subject dies (all causes other than VTE-related) after withdrawing from the study and reported on Day 210 but event time is prior to Day 180, then this event and corresponding time to death will be included in the all-cause mortality endpoint analysis
 - b. If a subject does not experience any efficacy composite endpoint event (primary or secondary) in the study, then this subject will be censored. The time to censoring is defined as the time from randomization to the minimum of (last day of their complete assessment for study outcomes during the double-blind period/Day 180 [double-blind withdrawal date for those who withdrew], or death date [censored at death date for analysis not related to the specific death endpoint]).

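### Non-VTE deaths after early withdrawal have two censoring dates, and under one of them the competing-risk analysis loses those deaths

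*SAP*

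**What the plan says.** Section 5.3 states, for the primary composite, that "a death due to causes other than VTE-related is a competing risk event", with no exception for deaths after withdrawal. Gray's test, the Fine and Gray model and the cumulative incidence functions all use the Up-to-Day 180 "observation period for the ITT population with censoring as defined above in Section 2.6".

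Section 2.6.1 then gives two statements on the date:

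- The general sentence: "Subjects who died during this observation period will be censored as of their death date for endpoint analyses not related to death".
- The censoring-time formula: the "minimum of (last day of their complete assessment for study outcomes during the double-blind period [double-blind completion/withdrawal], death date", with the death term qualified as "death date [non VTE-related deaths for primary efficacy composite endpoint" in its bracket.

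Section 2.5 sets the end of the Up-to-Day 180 period at the death date for subjects who "died post withdrawal from DB but before Day 180/EODB visit". For other early withdrawals it uses "Maximum (double-blind withdrawal date, randomization date + 180 days) for subjects who withdrew early from the double-blind period".

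Section 4.6 (2a) includes a VTE event in the primary analysis if it occurs "after withdrawing from the study and the time to the occurrence of the event is prior to Day 180". The same item assigns non-VTE deaths after withdrawal to the all-cause mortality analysis and does not mention competing risks. Section 4.6 (2b) restates the minimum formula and adds a bracket that again points to the death date.

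**The concern.** A death after withdrawal but before Day 180 is a case the SAP foresees, since 2.5 names it. Yet two programmers could follow the SAP faithfully and give the same subject different times and status codes in the Gray and Fine and Gray analyses.

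The choice has consequences. Section 5.3 exists so that non-VTE deaths are not handled as ordinary censoring. Under the formula, those that follow withdrawal still are. Follow-up after withdrawal also becomes selective: it continues for subjects who have a VTE and stops at withdrawal for those who do not.

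The group may not be small. Sections 1.2 and 1.4 report discontinuation high enough to raise the target from about 700 to about 800. Section 1.5 says that pancreatic subjects are more likely to leave early and that more than the planned 25% were allowed in.

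**Working it through.** **Figures in the plan.** The SAP gives no figure for the competing-risk analysis. From section 1.4 come the assumed 180-day rates (14.5% placebo, 6.0% rivaroxaban) and the 20% dropout. The stated sample size reproduces (280 evaluable per arm give 91.5% power) and does not bear on this point.

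**One subject under each rule.** Take withdrawal on Day 60, non-VTE death on Day 100 and no VTE.

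- Formula in 2.6.1: min(60, 100) = Day 60, censored. The death is not a competing event.
- Death sentence in 2.6.1: Day 100, where 5.3 makes the death a competing event.
- Section 2.5: the observation period ends on Day 100, so the death lies inside it.
- Had the same subject had a VTE on Day 100 instead, 4.6 (2a) would count it.

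The conflict arises only for subjects who withdraw and then die of a non-VTE cause before Day 180. Withdrawn survivors have a single date, the withdrawal date.

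**Size.** Times were simulated with exponential hazards, 1,000,000 subjects per scenario, and 180-day cumulative incidence was estimated by Aalen-Johansen. The following ranges are assumptions, not SAP figures: withdrawal 20-40%; non-VTE death 10-25% at 180 days on study; death hazard after withdrawal 1-3 times that before; 30-100% of post-withdrawal VTE captured. Both arms had the same withdrawal and death rates. The corners of the grid, in per cent, were:

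| Withdrawal / death / hazard ratio / VTE capture | Arm | True | Formula | Deaths counted only | Formula minus deaths counted |
|---|---|---|---|---|---|
| 20 / 10 / 1 / 100 | placebo | 13.79 | 15.20 | 15.09 | 0.11 |
| | rivaroxaban | 5.71 | 6.34 | 6.29 | 0.05 |
| 20 / 10 / 1 / 30 | placebo | 13.81 | 14.23 | 14.12 | 0.11 |
| | rivaroxaban | 5.70 | 5.88 | 5.84 | 0.04 |
| 40 / 25 / 3 / 100 | placebo | 12.24 | 15.28 | 13.73 | 1.55 |
| | rivaroxaban | 5.01 | 6.34 | 5.67 | 0.67 |
| 40 / 25 / 3 / 30 | placebo | 12.24 | 13.44 | 12.06 | 1.38 |
| | rivaroxaban | 5.05 | 5.59 | 5.01 | 0.58 |

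Across the grid, about 4 to 50 non-VTE deaths per 400 subjects fall after withdrawal.

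**Is counting the deaths enough?** In the first scenario it removes 0.11 of an error of 15.20 − 13.79 = 1.41 points. In the third it removes 1.55 of 15.28 − 12.24 = 3.04 points. A separate scenario assumed 30% withdrawal, 10% non-VTE death in the double-blind period and 50% 180-day mortality after withdrawal. For the 14.5% arm:

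- Post-withdrawal VTE fully captured: true about 13.5%, formula 15.8%, deaths counted only 14.8%. The error falls from 2.3 to 1.3 points. Competing-death incidence is truly about 15.6% but becomes 17.4%, so it is now overstated.
- None captured: true 13.4%, formula 13.7%, deaths counted only 12.9%. The error goes from +0.3 to −0.5 points.

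The remaining error arises because follow-up is extended only for subjects who have an event, while withdrawn survivors still leave at withdrawal.

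**Ratio between arms.** In that scenario it is 6.6/15.8 = 0.418 under the formula and 6.2/14.8 = 0.419 with deaths counted. In the third table scenario it is 6.34/15.28 = 0.415 and 5.67/13.73 = 0.413.

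**The case against.** The strongest reply is that the SAP does not say these deaths are excluded. The definition in 5.3 is unrestricted, 2.5 carries the period to the death date, and the death sentence in 2.6.1 agrees. A reader might infer from the formula that the deaths are definitely lost. That goes too far: the loss follows from one of two conflicting rules. What stands is the conflict itself and the loss under the formula.

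A reader might also infer that the comparison between arms is biased. The calculations do not show this, since the ratio stays close to 0.42 under either rule. They do assume equal withdrawal and mortality in both arms, and neither Gray's test nor the Fine and Gray estimate was simulated.

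A third inference would be that many subjects withdraw because they are dying. The SAP does not say so. Where death is itself the reason for leaving, the double-blind end date is the death date and the two rules coincide.

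Finally, the analysis lies outside the testing hierarchy in section 5.5. That is correct and limits the weight of the point.

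**Conclusion.** The point holds as an inconsistency in a pre-specified rule. Sections 2.6.1 and 4.6 (2b) give two censoring dates for non-VTE deaths after early withdrawal, and the formula imported by 5.3 removes those deaths as competing events. With post-withdrawal VTE still counted and event-free withdrawn subjects leaving at withdrawal, VTE cumulative incidence is overstated and competing-death incidence understated.

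The lost deaths alone account for about 0.1 to 1.6 points in the placebo arm and 0.04 to 0.7 points in the rivaroxaban arm. These sizes rest on assumed withdrawal, mortality and capture rates. The contradiction rests on the text alone. The effect is on absolute incidence in a supportive analysis, with little effect on the ratio between arms. It should be corrected, but it does not by itself call the primary log-rank result into question.

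**What to change.** - **Section 5.3, deaths.** Code a non-VTE death through the Up-to-Day 180 end date, without prior VTE, as a competing event on the death date, including after withdrawal.
- **Section 5.3, withdrawn survivors.** Where VTE and vital status are known from the Day 210 contact, censor at the Up-to-Day 180 end date. Censor at withdrawal only where that follow-up is missing. With complete follow-up nobody is censored early, and the asymmetry disappears.
- **Sections 2.6.1 and 4.6 (2b).** State one censoring date so that the sentence, the formula and the bracket agree. The primary Kaplan-Meier, log-rank and Cox analyses also take their censoring from 2.6, so settle the wording before unblinding and say which analyses it governs.
- **Deaths known only from registries.** Sections 1.2.1 and 4.6 promise vital status for these subjects, not cause of death or VTE history. State how such deaths are classified. Some error will remain here, because the death is known and an earlier VTE may not be.

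The cost is a few sentences and minor reprogramming. Vital status and outcomes at Day 210 are already collected, and deaths after withdrawal already enter all-cause mortality. The one real difficulty is unknown cause of death.
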